6.1.2. Analysis of the Primary Efficacy Endpoint

The non-progression rate at Week 24 and 95% confidence interval (CI) will be estimated using Kaplan-Meier method through PFS analysis. The number and percentage of subject who had no progressive disease at Week 24 by counting will also be provided for each treatment group.

The analysis of PFS will be performed using the Kaplan-Meier method for the Full Analysis Set. Medians, Q1, Q3, the proportion of subjects who have no progression or death events at 24 and

48 weeks from the first dosing date will be provided along with corresponding 95% CIs. Kaplan-Meier curves for PFS will be provided by treatment group.

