### **Test Product, Dose, and Mode of Administration:**

GS-5829 tablets will be self-administered orally once daily, beginning on Cycle 1 Day 1 of the study and thereafter at approximately the same time each day until end of treatment. GS-5829 is supplied as 0.2 mg, 1 mg, 5 mg, and 10 mg tablets.

Enzalutamide capsules will be self-administered orally once daily beginning on Study Day 1 of the Dose Escalation portion and Dose Expansion portion (Group 2). Enzalutamide will be supplied as 40 mg capsules; subjects will self-administer 160 mg (4 × 40 mg capsules) once daily.

---

---

Reference Therapy, Dose, and Mode of Administration:	Not Applicable
Criteria for Evaluation:	Phase 1b and Phase 2
Safety:	Safety will be evaluated by assessment of clinical laboratory tests, physical examination, 12-lead ECG, vital signs measurements, and the documentation of AEs
Efficacy	Disease progression will be assessed according to PCWG2 criteria. Progression/Non-progression rate at Week 12, Progression free survival defined by the time from Study Day 1 to the date of death from any cause or the date of progressive disease which one is earlier, and overall survival will be measured.
Pharmacokinetics:	The following PK parameters for GS-5829 will be calculated as applicable: $C_{max}$ , $AUC_{last}$ , $AUC_{tau}$ , $C_{tau}$ , and $T_{max}$

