### **5.3. Dosage and Administration of GS-5829 and Enzalutamide**

GS-5829 tablets will be provided by Gilead Sciences, Inc. and will be taken orally. Initiation of treatment with the study drug will take place after enrollment and cohort assignment. Subjects will take their dose of study drug at approximately 24-hour intervals. To reduce inter-subject variability on efficacy and safety, subjects will be instructed to take GS-5829 approximately 1 hour before or 2 hours after a meal, unless otherwise specified by protocol. Grapefruit juice is prohibited while on study drug. In one or more monotherapy dose levels or in the monotherapy expansion (Group 1), on Day 1 of Cycle 2, approximately 10 subjects may be asked to administer GS-5829 in fed state with a standardized meal (~500 to 600 calories and ~30% of calories from fat). If evaluation of food effect cannot be performed on Cycle 2, Day 1, it may be performed at a visit after Cycle 2, Day 1 (where subject has taken at least 7 consecutive days of GS-5829), if necessary.

XTANDI® (enzalutamide) will be supplied as 40 mg capsules for oral administration. Subjects assigned to receive enzalutamide in combination with GS-5829 in this study will orally self-administer 4 capsules of enzalutamide (160 mg total daily dose) once daily at approximately 24-hour intervals beginning on Study Day 1 and GS-5829 will start, at the assigned dose, 14 days ( $\pm$  3 day window) later on Cycle 1 Day 1. Subjects enrolled into Group 3 should be on at least 12 weeks of continuous enzalutamide treatment prior to starting Cycle 1 Day 1. Capsules should be swallowed whole and may be taken with or without food. Refer to [Appendix 9](#) for further details.

If the subject misses a dose, he should be instructed to take the study drug as soon as he remembers, unless more than 8 hours have elapsed since the scheduled time of the missed dose. In this case, the subject should be instructed to wait and take the next dose at the regularly scheduled time. Subjects should not take more than 1 dose of study drug at a time.

If a subject vomits within 5 minutes of dosing and the tablet is visible, the subject should be instructed to re-dose. If a subject vomits more than 5 minutes after dosing or if the tablet is not visible, the subject should be instructed to wait and take the next dose at the regularly scheduled time.

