**Phase 1b Dose Escalation and Phase 2 Dose Expansion:**

- PSA response:  $\geq 30\%$  decline in PSA from baseline at 12 weeks for Groups 1, 2 and 3
- Progression free survival (PFS) defined as the interval from first dose date of study drug to the earlier of the first documentation of definitive disease progression (assessed per PCWG2) or death from any cause.

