3.1.2. Full Analysis Set

The Full Analysis Set (FAS) includes all subjects who took at least 1 dose of study drug with treatment group designated according to the planned treatment. This is the primary analysis set for efficacy analyses. Throughout this SAP, study drug is defined as any drug in the therapy (GS-5829 or enzalutamide) unless specified otherwise.

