6. EFFICACY ANALYSES

6.1. Primary Efficacy Endpoint

6.1.1. Definition of the Primary Efficacy Endpoint

The primary efficacy endpoint of this study is non-progression rate at Week 24 defined as the proportion of subjects who don't progress by Week 24. The progression is determined by the investigators based on Prostate Cancer Working Group 2 (PCWG2) Criteria for lesion scans, bone scans and PSA assessments together. Subjects will be considered as having definitive disease progression if any of three progression criteria meets. Progression-free survival (PFS), defined as the interval from start of study drug to the earlier of the first documentation of definitive disease progression or death from any cause. Definitive disease progression is determined by investigator based on PCWG2 criteria.

The date of definitive progression will be the time point at which progression is first identified. The death from any cause to be considered as PFS event should occur within the time window of 2 consecutive scheduled tumor assessments after the last tumor assessment. Non-evaluable (NE) and no disease (ND) are considered as not adequate.

Subjects will be censored on the date of Study Day 1 if

- no adequate baseline target lesion assessment nor bone scan is available (note: baseline PSA assessment missing is allowed) and subject didn't die before or on the 2nd scheduled post-baseline tumor assessment without receiving anti-cancer therapy;
- or if no adequate post-baseline tumor assessment is available and subjects didn't die
- or if no adequate post-baseline tumor assessment is available and subjects died after the 2nd scheduled tumor assessment.

Subjects will be censored on the date of last adequate post-baseline tumor assessment, or Day 1 if the last post-baseline adequate tumor assessment doesn't exist, for the following situations:

- who do not have documented progression or die, or
- who start new anticancer therapy before documented progression, or
- who start new anticancer therapy before death without documented progression, or
- who have ≥ 2 consecutive missing post-baseline tumor assessments immediately before documented progression, or
- who have ≥ 2 consecutive missing post-baseline tumor assessments immediately before death without documented progression

Table 6-1 below provides detailed event/censoring scheme for PFS derivation and the derivation diagram provides all decisions on event/censoring indicators and time.

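### If CT/MRI runs from Cycle 1 Day 1, the combination cohorts' Week-24 and Week-48 Kaplan-Meier rates are read before the scans scheduled for those weeks

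*SAP*

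**What the plan says.** **Time origin.** SAP 6.1.1 has PFS "defined as the interval from start of study drug to the earlier of the first documentation of definitive disease progression" or death. SAP 3.1.2 adds: "Throughout this SAP, study drug is defined as any drug in the therapy (GS-5829 or enzalutamide) unless specified otherwise". The protocol agrees. Section 8.1.3 has PFS "defined as the interval from first dose date of study drug to the earlier of the first documentation of definitive disease progression" or death, and the synopsis (Criteria for Evaluation) has "Progression free survival defined by the time from Study Day 1 to the date of death from any cause" or progression.

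**Landmarks.** SAP 6.1.2 states: "The non-progression rate at Week 24 and 95% confidence interval (CI) will be estimated using Kaplan-Meier method through PFS analysis". It reports event-free proportions at 24 and "48 weeks from the first dosing date will be provided along with corresponding 95% CIs". A second rate is planned: "The number and percentage of subject who had no progressive disease at Week 24 by counting will also be provided for each treatment group". No time origin or window is given for that count.

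**Dosing and visits in combination.** Protocol 5.3 has enzalutamide "beginning on Study Day 1 and GS-5829 will start, at the assigned dose, 14 days" later, with a ±3-day window, on C1D1. Protocol 6.5 ties on-study visits to C1D1. Protocol 6.5.4 and the Appendix 3 table allow ±7 days. Appendix 3, footnote 16, refers CT/MRI to C1D1 at screening and then every 12 weeks. Protocol 6.2.9.2 repeats the 12-week interval during treatment but names no starting point. PSA is drawn before dosing on Day 1 of every 28-day cycle (Appendix 3, footnote 13).

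**The concern.** In combination cohorts the analysis clock starts about two weeks before the visit clock. A rate labelled Week 24 on the first clock can therefore be read before the Week-24 scan on the second. Progression first seen at that scan is dated after the landmark and left out of the rate. The same applies at Week 48.

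Two things are at stake. The combination rate reads high relative to disease status at the assessment whose name it carries. And the combination and monotherapy rates in the same table rest on different numbers of scheduled scans: in monotherapy the first dose is C1D1, so some subjects' Week-24 scans fall on or before the read. The counted rate may pick up the scan through the nominal-visit rule in SAP 3.8.2. That rule covers by-visit summaries and does not name the count, so the two Week-24 rates could disagree without explanation.

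**Working it through.** **The plan's own figure.** The only design figure for this rate (Protocol 8.9, SAP 1.3) says that more than 10 of 20 non-progressors puts the lower 90% bound above 30%. It reproduces: the exact 90% interval for 11/20 is 34.7% to 74.1%. It does not bear on timing.

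**Calendar** (days = event date minus first-dose date). Inputs: gap to C1D1 of 14 ± 3, so 11 to 17 days; visit window ±7 days; reads at 24 × 7 = 168 and 48 × 7 = 336.

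- Combination, C1D1 clock, Week-24 scan: earliest 11 + 168 − 7 = 172, latest 17 + 168 + 7 = 192. Both exceed 168.
- Week-48 scan: earliest 11 + 336 − 7 = 340, latest 17 + 336 + 7 = 360. Both exceed 336.
- The minimum gap (11 days) is larger than the early allowance (7 days), so no permitted combination of windows brings the scan before its read.
- Last scheduled PSA before day 168: C6D1, from 11 + 140 − 7 = 144 to 17 + 140 + 7 = 164. C7D1 falls on days 172–192.
- Monotherapy, or combination scans on a Study Day 1 clock: 168 ± 7, so days 161–175. Only scans after day 168 are missed.

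**Size.** Assumption: exponential time to progression from first dose, S(w) = S(24)^(w/24), with visits at nominal times. The last scheduled scan before day 168 is nominally at day 14 + 84 = 98 (week 14). The last PSA is at day 14 + 140 = 154 (week 22). For a true S(24) of 30%:

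- PSA finds everything: 0.30^(22/24) = 33.2%.
- Scheduled scans only (bone scans also on the C1D1 clock): 0.30^(14/24) = 49.5%, the ceiling.
- 20% of events dated continuously (deaths, unscheduled scans): 0.2 × 0.30 + 0.8 × 0.332 = 32.5%, up to 0.2 × 0.30 + 0.8 × 0.495 = 45.6%.
- Scans only, on a Study Day 1 clock, half of them late: (S(12) + S(24))/2 = (0.548 + 0.300)/2 = 42.4%.

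For a true 50%, the first two become 53.0% and 66.7%. At Week 48 a true 9% (0.30²) reads 0.09^(46/48) = 10.0% to 0.09^(38/48) = 14.9%.

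**In subjects.** The shift for a true 30% is 3 to 19.5 points. In cohorts of 3 to 6 that is 0.03 × 3 = 0.1 to 0.195 × 6 = 1.2 subjects.

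**A read at window close** (day 192 in combination). Visit-detected progression: 0.30^(26/24) = 27.1%. Continuously dated events: 0.30^(192/168) = 25.3%. The next scheduled PSA, C8D1, is no earlier than 11 + 196 − 7 = 200, so no later scheduled assessment enters. In a simulation of 200,000 subjects with uniform windows and scan-only detection, the read falls from 27% to 25% or 22% when 25% or 50% of those clean at the Week-24 scan have no later assessment and are censored there.

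**The case against.** **The anchor is not certain.** Protocol 6.2.9.2 names none, Protocol 6.2.9.1 uses Study Day 1 for the combination bone-scan screening window, and in Appendix 3, footnote 16, C1D1 appears only in the screening parenthesis. This stands. A reader might infer that the scan can never count toward its landmark. The documents support that only on the C1D1 clock, which Protocol 6.5 favours. On a Study Day 1 clock what remains is the boundary problem that monotherapy has.

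**The estimator does what it says.** PFS is defined by first documentation, so a read at day 168 does estimate documented events by 24 weeks from first dose. This stands too. The rate is high relative to status at the Week-24 assessment, not wrong for its own definition.

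**Other detection routes.** Any of three criteria counts as progression, including PSA each cycle. Deaths, end-of-treatment scans and unscheduled scans also count. A reader might take 49.5% as the expected reading. It is a ceiling that sets all of these aside, and they pull the rate toward the low end.

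**Moving the landmark can do worse.** It is tempting to replace the planned read. With 80% PSA-detected and 20% continuously dated events, a true 30% reads 32.5% now and 0.8 × 0.271 + 0.2 × 0.253 = 26.7% at day 192. The errors are +2.5 and −3.3 points, so the documents give no ground for replacing one read with the other.

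**What does not fall away.** No SAP rule shifts the landmark, adds the scan window or ties the counted rate to an assessment.

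**Conclusion.** The mismatch holds for combination cohorts, on condition that CT/MRI follows the C1D1 clock. The Week-24 and Week-48 scans then come 4 to 24 days after the reads that carry their names. Under assumed exponential times a true 30% reads between about 33% and a ceiling of 49.5%. The position in that range depends on the share of progression detected by scan, which the documents do not give.

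The point is minor. A reader might infer that the trial's primary conclusion is affected, but the documents do not support that. Phase 2, whose primary endpoint this is, was not opened (SAP 1). The Phase 1b primary endpoint is DLT incidence (Protocol 8.1.2), and no formal testing is planned (SAP 3.5). Only descriptive Phase 1b efficacy is touched, by about one subject or less per dose cohort.

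**What to change.** In SAP 6.1.2:

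- Keep the planned 24- and 48-week reads from first dose.
- Add a Kaplan-Meier read at the close of the scheduled assessment window: days 192 and 360 in combination, days 175 and 343 in monotherapy. Label each with its actual time from first dose.
- Define the counted rate by status at the nominal Week-24 assessment.

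The cost is a few sentences and one extra row per landmark, with no new data. The added combination read covers up to 192/7 = 27.4 weeks, so it reads somewhat low: about 25–27% for a true 30%, and lower if subjects are censored at a clean Week-24 scan. Under the assumptions above the two reads bracket the rate. Because the added landmarks differ by arm, the labels are essential.

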6.2. Secondary Efficacy Endpoints

6.2.1. Definition of Secondary Efficacy Endpoints

PSA response, defined as $\geq 30\%$ decline in PSA from baseline at 12 weeks.

Overall response by lesion scan only: subjects will be categorized based on PCWG2 criteria of lesion scans (same with RECIST v. 1.1 for lesion scans) as complete response (CR), partial response (PR), stable disease (SD), non-complete response or non-progressive disease, progressive disease (PD) or not evaluable (NE) at each visit of assessment.

Overall survival (OS), defined as the interval from start of study drug to death from any cause. Subjects who are lost to follow-up or survived until the end of the study will be censored at the last date that they were known to be alive.

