### 4.2. Inclusion Criteria

Subjects must meet all of the following inclusion criteria to be eligible for participation in this study.

- 1) Male  $\geq$ 18 years of age
- 2) Histologically or cytologically confirmed prostate cancer (subjects with primary neuroendocrine carcinoma of prostate are excluded)
  - Phase 1b Monotherapy Escalation: Subjects must have documented progressive disease by meeting at least one of the PCWG2 criteria ([Appendix 4](#)) despite treatment with abiraterone and/or enzalutamide
  - Phase 1b Combination Therapy Dose Escalation **and** Phase 2 Combination Dose Expansion (Group 2): Subjects must have documented progressive disease by meeting at least one of the PCWG2 criteria, despite treatment with abiraterone. They may **not** have received prior enzalutamide or chemotherapy for mCRPC
  - Phase 2 Monotherapy Dose Expansion (Group 1): Subjects must have documented progressive disease by meeting at least one of the PCWG2 criteria, despite treatment with enzalutamide. They may have received prior abiraterone, but not prior chemotherapy, for mCRPC
  - Phase 2 Combination Therapy Dose Expansion (Group 3): Subjects must have documented progressive disease by meeting the PCWG2 criteria for PSA progression, but not radiographic progression, despite treatment with enzalutamide. They may have received prior abiraterone, but not prior chemotherapy, for mCRPC (similar to Group 1); however, they must also have been on continuous enzalutamide therapy for at least 12 weeks days prior to Cycle 1, Day 1.
- 3) Castration-resistant disease defined as ongoing androgen deprivation therapy with GnRH analogue or bilateral orchiectomy and serum testosterone level  $\leq$  1.73 nmol/L (50 ng/dL) at screening visit. Subjects who have not had a bilateral orchiectomy must have a plan to maintain effective GnRH-analogue therapy for the duration of the trial.

- 4) Metastatic disease documented by bone lesions on bone scan or by measurable soft tissue disease by CT/MRI. Patients whose disease spread is limited to regional pelvic lymph nodes are not eligible
- 5) All acute toxic effects of any prior antitumor therapy resolved to Grade  $\leq 1$  before the start of study drug dosing (with the exception of alopecia [Grade 1 or 2 permitted] and neurotoxicity [Grade 1 or 2 permitted])
- 6) Eastern Cooperative Oncology Group (ECOG) Performance Status of  $\leq 1$
- 7) Life expectancy of  $\geq 3$  months, in the opinion of the Investigator

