**Appendix 4. Criteria of Progression for Trial Eligibility by Disease Manifestation (PCWG2, JCO 2008)**

Variable	Criteria
PSA	Obtain sequence of rising values at a minimum of 1-week intervals 2.0 ng/mL minimum starting value 

Estimate pre-therapy PSA-Doubling Time if 3 or more values available 4 or more weeks apart

Target lesions	Nodal or visceral progression sufficient for trial entry independent of PSA RECIST to record soft-tissue (nodal and visceral) lesions as target or non-target Only lymph nodes $\geq$ 2 cm in diameter should be used to assess for a change in size
Prostate	Directed pelvic imaging (CT, MRI, PET/CT, endorectal MRI, transrectal ultrasound) to document presence of absence of disease
Bone	Progression = appearance of 2 or more new lesions Confirm ambiguous results by other imaging modalities (eg, CT or MRI)
Other sites	Patients with treated epidural lesions and no other epidural progression are eligible

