## Appendix 5. On Study Outcome/Efficacy Criteria (PCWG2, JCO 2008)

Variable	Criteria
PSA	
Ignore early rises (prior to 12 weeks) in determining PSA response
 
For control/relieve/eliminate endpoints:
 

Percent change from baseline at 12 weeks and maximal change at any time using a waterfall plot.

 
For progression endpoints:
 

Decline from baseline: record start of therapy to first PSA increase that is <math>\geq 25\%</math> and <math>\geq 2</math> ng/mL above the nadir and confirmed by a second value 3 or more weeks later.

No decline from baseline: PSA progression <math>\geq 25\%</math> and <math>\geq 2</math> ng/mL after 12 weeks

Soft tissue	
Use RECIST with caveats:
 

Only report changes in lymph nodes that were <math>\geq 2</math> cm in diameter at baseline

Record changes in nodal and visceral soft tissue sites separately

Record complete elimination of disease at any site separately

Confirm favorable change with second scan

Bone	
The appearance of <math>\geq 2</math> new lesions, and, for the first reassessment only, a confirmatory scan performed <math>\geq 6</math> weeks later that shows <math>\geq 2</math> additional new lesions
 
The date of progression is the date of the first scan that shows the change

---

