6.2.2. Analysis Methods for Secondary Efficacy Endpoints

Number of subjects with $\geq 30\%$ or $\geq 50\%$ PSA reduction from baseline at 12 weeks and during the whole treatment period will be summarized separately.

The number and percentage of subjects in each overall response category by lesion scans (eg, CR, PR, SD, and PD) will be summarized by treatment group for the FAS.

The analysis of OS will be performed using the Kaplan-Meier method for the FAS Analysis Set. Medians, Q1, Q3, the proportion of subjects who have no events at 24 weeks and 48 weeks from the first dosing date will be provided along with corresponding 95% CIs. Kaplan-Meier curves for OS will be provided by treatment group.

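### SAP 6.2.1 equates the PCWG2 lesion criteria with RECIST 1.1 and so drops the protocol's Appendix 5 caveats, including confirmation of a response on a second scan

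*SAP*

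**What the plan says.** Protocol 6.2.9.2 has response after baseline assessed by PCWG2 and refers the reader to Appendix 5. The soft-tissue entry there opens with "Use RECIST with caveats" and lists four:

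- "Only report changes in lymph nodes that were" at least 2 cm across at baseline. Appendix 4 has a matching rule for eligibility: only nodes of at least 2 "cm in diameter should be used to assess for a change in size".
- "Record changes in nodal and visceral soft tissue sites separately".
- Complete elimination of disease at any site is recorded separately.
- "Confirm favorable change with second scan".

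SAP 6.2.1 defines overall response by lesion scan from "PCWG2 criteria of lesion scans (same with RECIST v. 1.1 for lesion scans" and closes the parenthesis there. Each assessment visit receives one of CR, PR, SD, non-CR/non-PD, PD or NE. Under SAP 6.2.2 the number and percentage of subjects in each category "will be summarized by treatment group for the FAS".

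The FAS is every subject who took at least one dose of study drug (SAP 3.1.2). Inclusion criterion 4 in Protocol 4.2 asks for "Metastatic disease documented by bone lesions on bone scan or by measurable soft tissue disease by CT/MRI", so bone lesions alone are enough for entry.

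**The concern.** RECIST with four stated modifications is not the same thing as RECIST. The SAP asserts that it is, and does not present this as a change from the protocol. A programmer working from SAP 6.2.1 and 6.2.2 would find no confirmation step, no node-size rule and no separate nodal and visceral record. A CR or PR on a single scan would enter the table as a response, although Appendix 5 asks for a second scan.

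Efficacy by PCWG2 criteria is a phase 1b secondary objective. The SAP Introduction states that the study stopped without opening phase 2, so phase 1b is the only source of efficacy data.

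A smaller, related matter is how the table reads. It covers the whole FAS, and some of those subjects may have had no soft-tissue lesion in which a response could appear. SAP 6.1.1 recognises a no-disease scan result, but the list in SAP 6.2.1 has no such category.

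**Working it through.** The documents give no lesion response rate, precision or sample size, so there is no figure to reproduce. The check is a comparison of texts, followed by arithmetic on assumed inputs to show direction.

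**Step 1: the rules side by side**

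| Rule | Protocol Appendix 5 | SAP |
|---|---|---|
| Base criteria | RECIST (version not named) with caveats | Stated to be the same as RECIST 1.1 |
| Node size | At least 2 cm at baseline | Not stated |
| Nodal and visceral change | Recorded separately | Not stated |
| Complete elimination at a site | Recorded separately | Not stated |
| Favorable change | Second scan needed | Category assigned at each visit; no confirmation step |

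**Step 2: one subject followed through.** Scans are every 12 weeks (Protocol 6.2.9.2). Take a subject with PR at Week 12 that is gone at Week 24. SAP 6.2.1 assigns PR at Week 12, and SAP 6.2.2 counts a subject in the PR row, whether that table is by visit or by best category (the SAP does not say which). Under Appendix 5 the favorable change was never confirmed.

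**Step 3: direction.** Let

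- r = proportion with CR or PR on at least one scan, among subjects with measurable soft-tissue disease;
- c = share of those responses that are confirmed;
- m = share of the FAS with measurable soft-tissue disease.

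None of the three is given. I assume that the remaining subjects contribute no CR or PR. Then:

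- SAP as written: m × r
- confirmed, over the FAS: m × r × c
- confirmed, over measurable subjects: r × c

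With r = 20% and c = 70%, both assumed:

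| m | SAP as written | Confirmed, FAS | Confirmed, measurable |
|---|---|---|---|
| 100% | 20% | 14% | 14% |
| 70% | 14% | 9.8% | 14% |
| 50% | 10% | 7% | 14% |
| 30% | 6% | 4.2% | 14% |

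For c = 50% and 90%, the last column is 0.20 × 0.50 = 10% and 0.20 × 0.90 = 18%.

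Over the FAS, the SAP figure exceeds the confirmed figure by the factor 1/c, so omitting confirmation can only add responses. Against the confirmed rate in measurable subjects the ratio is m/c. That is above 1 when m > c, equal to 1 when m = c (the 70% row), and below 1 when m < c. The two effects oppose each other, and the documents do not show which is larger.

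**Step 4: cohort scale.** Escalation cohorts have 3 to 6 subjects (Protocol 3.2). In a cohort of 6 with 3 subjects lacking measurable disease, one responder is 1/6 = 17% of the FAS and 1/3 = 33% of measurable subjects. If the response is not confirmed, both are zero.

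**Step 5: node rule.** The documents do not reproduce RECIST 1.1, so I make no claim about its node threshold. Leaving out smaller nodes can remove either shrinkage or growth, so this effect has no determinable direction.

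**The case against.** The SAP still names PCWG2 as the criteria, so the caveats arguably come with the name, and a per-visit category merely describes that scan. That lessens the fault without removing it. The parenthesis tells the reader what PCWG2 means for lesion scans, and its answer is plain RECIST 1.1. The table in SAP 6.2.2 then counts subjects by those categories with no confirmation step.

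On importance the objection largely stands. Lesion response is not among the endpoints in Protocol 8.1.3, no formal testing is planned (SAP 3.5), and escalation is governed by DLTs.

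Four stronger readings are tempting, and the documents do not support them:

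- **Subjects with bone disease only have no valid category.** SAP 6.2.1 lists non-CR/non-PD and NE. Only a no-disease label is missing.
- **The Week 24 progression endpoint is contaminated by growth in small nodes.** SAP 6.1.1 relies on investigator-assessed PCWG2 and does not repeat the RECIST 1.1 equation. Protocol 6.2.9.2 points investigators to Appendix 5, which has the node rule.
- **The FAS denominator is an error.** Protocol 8.2.1.1 prescribes the FAS for efficacy endpoints, and counts appear beside percentages. A measurable-disease percentage is a useful supplement and does not correct a mistake.
- **The percentages mainly reflect how many bone-only subjects were enrolled.** Criterion 4 permits entry on bone lesions, but does not say that such subjects lack soft-tissue disease, and their number is not given.

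**Conclusion.** The statement in SAP 6.2.1 is wrong as written. It contradicts Protocol Appendix 5, and the resulting table would count unconfirmed CR and PR as response. This rests on the text alone, with no assumption about the content of RECIST 1.1.

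The size is not determinable. Over the FAS, missing confirmation can only inflate the CR/PR count. A share of subjects without measurable disease pulls the percentage down relative to the rate among those who could respond. The net effect depends on m and c, which the documents do not supply, and the percentages under working are illustrations only.

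The consequence is limited to a descriptive secondary readout. It should be corrected, but it affects neither dose escalation nor the definition of progression.

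**What to change.** In SAP 6.2.1, replace the parenthesis with the Appendix 5 rules: nodes of at least 2 cm at baseline, nodal and visceral change recorded separately, complete elimination at any site recorded separately, and CR or PR confirmed on a second scan. Appendix 5 sets no minimum interval for soft-tissue confirmation, so the SAP should say which later scan qualifies. Apply the node rule as far as recorded baseline diameters allow. The eCRF is not among the documents, so whether they were recorded needs checking.

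In SAP 6.2.2:

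- tabulate confirmed CR and PR, with unconfirmed CR and PR shown separately;
- keep the FAS table and add a row for no disease or no measurable soft-tissue disease;
- add a supplementary percentage among FAS subjects with measurable soft-tissue disease at baseline.

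SAP 6.1.1 needs no change.

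The cost is SAP wording, a confirmation derivation and one baseline flag. No new scans are required. The SAP Introduction allows changes after finalization to be documented in the CSR. The price is fewer counted responses and very small supplementary denominators, which should be shown as counts beside the percentages.
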